1.2 Study objectives

Primary objective

To describe the efficacy of alpelisib as measured by the proportion of patients with response (yes/no) at Week 24 or 6 months (+/- 4 weeks), defined by achieving at least 20% reduction from index date in the sum of measurable target lesion volume (1 to 3 lesions, via central review of imaging scans), provided that none of the individual target lesions have $\geq 20\%$ increase from index date and in absence of progression of non-target lesions and without new lesions.

Secondary objectives

1. To assess changes in the sum of measurable target lesion (1 to 3 lesions) volume over time
2. To assess changes in the sum of all measurable (target and non-target) lesion volume over time
3. To assess changes in the sum of all measurable non-target lesion volume over time
4. To assess the duration of response defined as the time from first documented response, to the date of the first documented disease progression or death due to any cause.
5. To assess type of medication and non-drug therapies (e.g., concomitant PROS-related medications, PROS-related surgeries, duration of treatment/response) over time
6. To assess changes in PROS symptoms and complications (e.g., chronic bleeding/leaking, pain) over time
7. To assess changes in functional status (e.g., work/school/pre-school attendance, mobility) over time
8. To assess changes in HRU (e.g., ER visits, hospitalizations) over time
9. To assess changes in clinical assessments such as laboratory evaluation, vital signs and physical findings over time
10. To assess the safety and tolerability of alpelisib

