3.2 Analysis population(s)

The **full study population** will include all patients that satisfy the study inclusion criteria. This population set will be used for all secondary [REDACTED] efficacy analyses and for safety analyses.

The **efficacy population** is a subset of the full study population, which will be used for the analysis of the primary endpoint and includes patients who meet the following criteria:

- Patient had at least one target lesion
- Patient had an imaging scan performed on the index date (or up to 24 weeks prior to the index date) for at least one target lesion

3.3 Key post index date time points for reporting endpoint over time.

Considering the retrospective nature of the study, patients might have data available at different time-points. In order to maximize the use of data abstracted, key time points and associated time windows are identified for reporting purpose. For each of these time-points or intervals all patients with data available will be used. The total number of patients in a time interval will be equal to the number of patients with at least one valid assessment in that specific time window. The number of patients (N) in each interval will be summarized in the disposition table and used throughout the report. Only the time points with data available for at least 10% of the patients will be displayed in the corresponding output.

Key study time points are summarized in [Table 3-1](#).

Table 3-1 Time windows for post-index date key-time point

Key time-points	Allowed windows
4 weeks	Up to 10 weeks
12 weeks	[10 to 20 weeks[
24 weeks*	[20 to 32 weeks[
36 weeks	[32 to 40 weeks[
52 weeks	[40 to 58 weeks[
End of study	4 weeks prior to and up to min(study treatment discontinuation + 30 days, cut-off date)

* 24 weeks or 6 months (+/- 4 weeks).

After week 52 intervals of approximately 11 weeks (e.g. 63 weeks, 74 weeks, etc.) with a time window of +/- 5 weeks will be used until the "end of study".

Week 24 windows (+/- 4 weeks) is intended to include assessments performed 24 weeks or 6 months after index date, where 6 months is approximated to week 27.

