For the Wong Baker scale, “improvement” is defined as a decrease by at least 2 points and worsening is defined as an increase by at least 2 points. For the FLACC and the Numerical scales, an “improvement” is defined as a decrease by at least 1 point and worsening is defined as an increase by at least 1 point. Results from other scales will be listed, if reported.

To further assess pain reduction at week 24 time point the following items will be summarized at index date and between week 24 or 6 months (+/- 4 weeks): concomitant medications used for pain excluding opioids; opioids; medical conditions/treatment emergent adverse events (by grade) related to pain; pain score from the questionnaire. A pain reduction will be flagged if improvement is reported for at least one of the following items provided that none of the other items is associated with a deterioration during the same period: pain score from the questionnaire, number of concomitant medications excluding opioids, number of opioids, number and severity of pain related medical conditions/treatment emergent adverse events.

To identify concomitant medications used for pain the following ATC will be selected:

1. M02 "TOPICAL PRODUCTS FOR JOINT AND MUSCULAR PAIN";
2. M03 "MUSCLE RELAXANTS";
3. N02 "ANALGESICS";
4. V10B PAIN PALLIATION";
5. M09AB01 "chymopapain".

To identify concomitant opioids used for pain the ATC code N02A "Opioids" will be used.

Current medical conditions/adverse events related to pain will be identified by selecting all Preferred Terms (PT) related to pain. The list of PT used to select pain will be identified by the clinical team and archived.

Table 3-5 Endpoints related to objective #6

Measure	Type of variable	Summary Statistics	Timing
Proportion of patients with symptom/complication/comorbidity overall and by severity	Binary	Frequency, percentage	At key time-points
Type of symptom/complication overall and by severity	Categorical	Frequency, percentage	At key time-points
Proportion of patients with “High”, “Medium” and “Low” impact symptoms/complications/comorbidities adverse events (see definition in section 3.6 Secondary endpoints) by primary	Categorical	Frequency, percentage	Overall

Measure	Type of variable	Summary Statistics	Timing
system organ class (SOC) and preferred term (PT)			
Proportion of patients with a pain assessment performed	Binary	Frequency, percentage	At index date

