Proportion of patients with improvement, worsening and stable in pain severity	Binary	Frequency, percentage	At key time-points
Pain reduction (indicator)	Binary	Frequency, percentage	At week 24 time-point

Endpoints related to secondary objective #7: Change in functional status

The following endpoints are included for analysis to describe any improvement in PROS patients being able to return to, or improve their attendance at work/school, as well as any change in their ability to undertake usual activities of daily living, such as improvements in mobility. It is anticipated that the data availability associated with these endpoints may not be consistent across all patients/sites; however it will be reported as available and utilized also to generate physician narratives.

The number of patients attending work/school/pre-school will be summarized at the index date and the percentage of patients reporting improvement, worsening or stable at each time-point will be reported. The reason for change of status will be listed where available.

Frequency counts and percentages will be presented for mobility assessments at the index date and at key time-points. Performance status scores (ECOG, Lansky, Karnofsky) will be reported appropriately by age category, at the index date and the percentage of patients reporting improvement, worsening or stable in score will be summarized at baseline, 12, 24 and 52 weeks windows as well as the "End of study".

For work attendance:

- "Improvement" is defined as a shift from reporting of "No attendance" to "Part-time" or "Full time", from "Part-time" to "Full-time", as well as from "Unemployed" to "Part-time" or "Full-time" work.
- "Worsening" is defined as a shift from reporting of "Part-time" to "No attendance", "Full-time" to "Part-time" or "No attendance" as well as "Part-time" or "Full-time" to "Unemployed" status.

Similarly, for school attendance:

- "Improvement" is defined as a shift from reporting of "No attendance" to "Part-time" as well as, "Part-time" or "No attendance" to "Full-time";
- "Worsening" is defined as a shift from reporting of "Part-time" to "No attendance", as well as from "Full-time" to "Part-time" or "No attendance".

Work attendance will only be reported for the adult patients (i.e., ≥ 18 years of age) while school attendance will be reported for both pediatric and adult patients

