For the ECOG scale, "improvement" is defined as a decrease by at least 1 point and "worsening" is defined as an increase by at least 1 point. For the Karnofsky and Lansky scale, "improvement" is defined as an increase by at least 20 points and worsening is defined as a decrease by at least 20 points. For example if a patient reports a score of 100 ("Normal, no complaints") at index date and a score of 80 ("Care for self. Unable to carry on normal activity or to do active work") would be considered as "worsening" while a score of 90 will still be considered as "stable". This approach takes into account the criteria for correspondence between the ECOG and Karnofsky/Lansky scale to make the categorization comparable and consistent between the scales. Results from other scales will be listed, if reported.

Importantly, based on feasibility discussions with study sites, it is anticipated that there will be variability in the use of the listed performance status measurement tools, based on preference of each institution, as well as variability on whether a performance measure is utilized for each patient (given the heterogeneity in the complications experienced by PROS patients).

Table 3-6 Endpoints related to objective #7

Measure	Type of variable	Summary Statistics	Timing
Proportion of patients that attend work/school/pre-school, overall and by type (i.e., full-time, part-time, no attendance)	Categorical	Frequency, percentage	At index date
Proportion of patients with "improvement", "worsening" and "stable" in work/school/pre-school attendance	Categorical	Frequency, percentage	At key time-points
Proportion of patients with any mobility assessments	Binary	Frequency, percentage	At key time-points
Severity of mobility impairment (i.e., no, mild, moderate, severe, total impairment)	Categorical	Frequency, percentage	At key time-points
Proportion of patients with a functional assessment (i.e., ECOG, Karnofsky, Lansky, other) performed	Binary	Frequency, percentage	At index date
Functional assessment score (ECOG, Karnofsky, Lansky)	Continuous	N, mean, median, standard deviation, Q1, Q3, minimum and maximum	At index date
Proportion of patients with "improvement", "worsening" and "stable" in functional assessment (ECOG, Karnofsky, Lansky)	Binary	Frequency, percentage	At key time-points

Endpoints related to secondary objective #8: Change in Healthcare resource use (HRU)

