3.6.2 Handling of missing data for the secondary endpoints

To report of the secondary endpoint all available data at that specific time point will be used. At each time point the total number of patients with available data will be shown. No imputation methods will be performed. If at the time point a parameter is missing for that patient it will not be reported.

[REDACTED]

4 Appendix

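### Non-pain PROS symptoms and mobility are summarised only as separate percentages per window, so change in patients cannot be told apart from change in who has data

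*SAP*

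**What the plan says.** SAP section 1.2 states objective 6 as "To assess changes in PROS symptoms and complications (e.g., chronic bleeding/leaking, pain) over time" and objective 7 as "To assess changes in functional status (e.g., work/school/pre-school attendance, mobility) over time".

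For symptoms and complications in general, Table 3-5 in SAP section 3.6 lists "Proportion of patients with symptom/complication/comorbidity overall and by severity", summarised by frequency and percentage at key time-points. For mobility, the text says "Frequency counts and percentages will be presented for mobility assessments at the index date and at key time-points", and Table 3-6 lists "Severity of mobility impairment (i.e., no, mild, moderate, severe, total impairment", again by frequency and percentage. No shift table, change category or restriction to paired patients is defined for either. Protocol section 6.8.2 speaks of change for both but also specifies only counts and percentages.

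On the base of these percentages, SAP section 3.3 says "The total number of patients in a time interval will be equal to the number of patients with at least one valid assessment" in that window, and adds "The number of patients (N) in each interval will be summarized in the disposition table and used throughout the report". SAP section 3.6.2 says "To report of the secondary endpoint all available data at that specific time point will be used", with no imputation and with a patient left out where the parameter is missing.

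**The concern.** A percentage at index and a percentage at week 52 measure change only if they describe the same patients. Here they need not. A falling percentage may mean that patients improved, or that affected patients were less often represented in the later window. A flat percentage may hide real improvement. The number shown per window tells the reader how many patients have data, not which ones, and with no control group nothing else reveals a drift in composition.

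The SAP gives these results real work to do. Section 3.6 includes the objective 6 endpoints so that efficacy on the primary endpoint can be linked to symptom improvement in the patient, and protocol section 6.8.1 describes efficacy from the totality of evidence. For bleeding, infections, seizures, fatigue and the other non-pain symptoms, no per-patient change is defined from which such a link could be tabulated.

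**Working it through.** **1. The plan's own figure.** The documents give no precision figure for symptoms or mobility. The only one for binary outcomes is protocol Table 6-2 (n = 50). The Clopper-Pearson exact 95% interval reproduces all four rows to three decimals; for 20/50 = 0.400 it gives 0.264 to 0.548, width 0.284, half-width 0.142.

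**2. Which measures have within-patient change (SAP section 3.6).**

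| Measure | Planned summary |
|---|---|
| Pain scales | improvement / worsening / stable |
| Pain reduction, week 24 | per-patient flag |
| Work and school attendance | improvement / worsening / stable |
| ECOG, Karnofsky, Lansky | improvement / worsening / stable |
| Laboratory values | shift from index to worst value |
| Other symptoms and complications | percentage per window |
| Mobility (five ordered levels) | percentage per window |

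The SAP version history shows that Amendment 3 replaced the percentage attending work or school by change categories. The same step was not taken for the last two rows.

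**3. Does the set of patients differ between windows?** Protocol section 6.9 notes that clinical practice has no common assessment schedule, and SAP section 3.6 expects uneven availability for objective 7. Data stop 30 days after treatment discontinuation (SAP section 1.3). The fixed cut-off also matters. A patient starting on 23-Sep-2019 has 168 days = 24 weeks to 09-Mar-2020. The 52-week window opens at 40 weeks (SAP Table 3-1), so reaching it needs a start at least (40 − 24) × 7 = 112 days earlier, about 3 June 2019. Later starters cannot contribute to it.

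**4. Effect if availability is related to status.** Inputs: N = 50 (planning figure, protocol section 6.6). The 40% prevalence at index (A = 20 affected, U = 30 unaffected) and the availability rates a (affected) and u (unaffected) are assumptions. Nobody changes state.

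Window percentage = A·a / (A·a + U·u)

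| a | u | Affected / all with data | Reads as | Shift from 40% |
|---|---|---|---|---|
| 0.9 | 0.9 | 18/45 | 40.0% | 0.0 |
| 0.7 | 0.9 | 14/41 | 34.1% | −5.9 |
| 0.5 | 0.9 | 10/37 | 27.0% | −13.0 |
| 0.9 | 0.7 | 18/39 | 46.2% | +6.2 |
| 0.9 | 0.5 | 18/33 | 54.5% | +14.5 |

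The outer shifts are about as large as the half-width of 14.2 points in step 1. A table pairing index with the window shows 0 improved and 0 worsened in every row.

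**5. The reverse case.** Suppose 6 of the 20 affected patients resolve, so the true percentage falls from 40% to 14/50 = 28%. If all 20 patients affected at index and half of the other 30 have data, the window reads 14/(20 + 15) = 40.0%, apparently no change. The paired table on those 35 patients shows 6 improved and 0 worsened.

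**The case against.** **Objectives 6 and 7.** A reader might infer that they go unanswered. The documents do not support that. Pain is itself a listed PROS symptom (protocol section 6.3.2) and has within-patient change; so do attendance and performance status. The gap is confined to the last two rows of the table in step 2.

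**Denominator.** A reader might also infer, from the interval N in section 3.3, that a patient seen only for a blood test counts as free of the symptom or impairment. On that reading, 6 affected of 12 assessed would fall from 6/12 = 50% to 6/40 = 15% on an interval N of 40 (illustrative numbers). The SAP does not say this. Section 3.6.2, which is specific to secondary endpoints, points the other way, and Table 3-6 reports the proportion with a mobility assessment in each window. What stands is an ambiguity about which base the percentages use.

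**Dated records.** Symptoms are recorded with start and end dates, and SAP Table 4-2 sets missing end dates, including ongoing events, to the end of the study period. An ongoing symptom may therefore carry into a window without a visit, so the availability model in step 4 fits mobility better than symptoms. This stands and shapes the fix. It does not close the gap, because the SAP does not say whether such a patient counts in the numerator or in N.

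**Evidence of selective availability.** The documents say that availability varies, not that it depends on status. Their nearest statement is that use of performance measures varies with the complications patients have (SAP section 3.6). The bias is thus a risk, not a finding.

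**Other safeguards.** Physician narratives are to discuss how lesion changes relate to function and symptoms (protocol section 6.3), data around discontinuation also enter the end-of-study window, and all secondary analyses are descriptive. These soften the consequence but provide no tabulated change.

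**Conclusion.** The point holds for PROS symptoms and complications other than pain, and for mobility. For these, the SAP plans percentages on changing sets of patients where the objectives ask for change, although it already classifies within-patient change for comparable measures.

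Under the assumed prevalence and availability rates, the percentage moves by −13.0 to +14.5 points with no patient changing; with equal availability it does not move. The direction and size in this study cannot be derived from the documents. Because the analyses are descriptive and other components of both objectives are sound, this is an improvement the sponsor should make, not a flaw that invalidates the secondary results.

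**What to change.** - **Mobility (Table 3-6).** Add index-to-week-24 and index-to-week-52 shift tables on the five ordered levels, summarised as improved, stable or worsened, in patients assessed at both times. Use the paired number as denominator.
- **Symptoms listed in protocol section 6.3.2 (Table 3-5).** At weeks 24 and 52, among patients still under observation in the window, report those with the symptom at index as resolved, less severe, same or worse, and those without it as new or still absent. Derive status from start and end dates and the abstracted severity, since no record is not an assessment of absence. State how records with a completely missing start date are treated: SAP section 4.3.1.1 assigns them to the study period unless they end before the index date, so they could read as new.
- **Denominator.** State that percentages use the parameter-specific number of section 3.6.2 and that the section 3.3 interval N is shown for information only.
- **Who is seen.** Show the index distribution of patients with and without data in each window.

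The data are already to be abstracted. The cost is additional tables, some sparse, with small and visible denominators. Missing severity will leave some symptoms classifiable only as present or absent. Pairing removes the change in case mix but not the bias that arises if patients who worsen stop being seen; the last item helps the reader judge that.

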### 6.2.1 Inclusion criteria

Patients will be included in this study if they meet all of the following inclusion criteria:

1. Patient (adult or pediatric) is $\geq 2$ years of age *
2. Patient has a physician confirmed/documented diagnosis of PROS*
3. Patient has a documented evidence of a mutation in the PIK3CA gene*
4. Patient's condition was assessed by the treating physician as severe or life threatening and treatment was deemed necessary*
5. Patient has been treated with at least one dose of alpelisib, initiated on or before 23-Sep-2019 (i.e. at least 24 weeks before the cut-off date of the 09-Mar-2020)
6. Patient has medical chart history available during enrollment in the MAP
7. Patient (in case of pediatric patients assent and/or parent/guardian consent) consented to participate in the study (as required by local ethics regulations)
* Inclusion criteria for MAP enrollment (assessed at the time of alpelisib initiation).

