#### Endpoints related to objective #7: Change in functional status

The endpoints for this objective will assess changes in functional status (i.e., work/school/pre-school attendance, mobility, and performance status) between the index date and key time-points following the index date (Table 6-1). The number (%) of patients attending work/school/pre-school will be summarized at the index date and at each time-point. In addition, the number (%) of patients with work/school/pre-school attendance (e.g., full-time; part-time, no attendance; part-time) will be presented at each time-point along with the reason for change status. Frequency counts and percentages will also be presented for the number (%) of patients with mobility between the index date and key time-points following the index date (Table 6-1). Performance status scores (i.e., ECOG, Lansky, Karnofsky) will be described and presented at the index date and at key time-points following the index date along with the number (%) of

patients with a change between the index date and key time-points following the index date (Table 6-1).

Endpoints related to objective #8: Change in HRU

The endpoints for this objective will assess changes in HRU (e.g., ER visits, hospitalizations) over time during the study period and key time-points following the index date (Table 6-1). The mean (SD) rate of hospitalizations and ER visits will be presented during the pre-index period and between the index date and over time during the study period. Frequency counts and percentages will also be presented for the number (%) of patients experiencing at least one hospitalization and at least one ER visit, separately, during the pre-index date period and study period. The mean (SD) number of ER visits and the mean (SD) duration of hospitalization will also be presented during the pre-index date period and over time during the study period.

Endpoints related to objective #9: Change in clinical assessments such as laboratory evaluation, vital signs and physical findings over time

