3.5.4 Subgroup analyses for the primary endpoint

The primary endpoint will be summarized and reported for the following subgroups:

- Age (e.g., 2-5; 6-11;12-17; 18+; pediatric patients and adults patients)
- Sex
- Mutation type (e.g., frequent, less frequent)
- PROS subtype (e.g., CLOVES, KTS)
- Lesion type (e.g., vascular, adipose)

Forest plots (Response %, 95% CI) will be produced to graphically depict the treatment effect estimates in different subgroups.

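### School attendance is scored from the category shift alone, so starting or finishing school is tabulated as improvement or worsening while the reason for the change is only listed

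*SAP*

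**What the plan says.** SAP 3.6, under secondary objective 7, sorts each patient's school attendance against the index-date category. The criterion for a better outcome reads: "is defined as a shift from reporting of 'No attendance' to 'Part-time' as well as, 'Part-time' or 'No attendance' to 'Full-time". Every downward move among the same three categories counts as worse. Work attendance is restricted to adults, but "school attendance will be reported for both pediatric and adult patients". Table 3-6 of the SAP includes pre-school in the same measure.

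On the reason for a change, the two documents differ. In protocol 6.8.2 (objective 7), the attendance categories "will be presented at each time-point along with the reason for change status". In SAP 3.6, "The reason for change of status will be listed where available". The SAP version history (Amendment 3) records the move from table to listing, so it was deliberate.

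On age, protocol 6.2.1 admits patients from 2 years. SAP 3.5.4 plans primary-endpoint subgroups by "Age (e.g., 2-5; 6-11;12-17; 18+; pediatric patients and adults patients". SAP 3.6 asks for performance status by age category but says nothing of the kind for attendance.

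**The concern.** SAP 3.6 gives the purpose of this endpoint as describing whether patients get back to work or school or attend more, and it presents the secondary endpoints as backing for efficacy. Attendance also changes because children grow up. Entry to pre-school or school, and completion of school, are ordinary events in the eligible age range, and the rule treats them exactly like a change caused by disease or treatment. There is no comparison group from which the expected rate of such transitions could be read. The recorded reason is the one planned data item that could separate the two kinds of change, and it is kept out of the table.

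**Working it through.** The documents state no figure for attendance, so there is none to reproduce. The check is of the rule itself, followed by an illustration of its leverage.

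**1. The rule.** Inputs: the three school categories and the two definitions in SAP 3.6. Three categories give 3 × 2 = 6 ordered shifts.

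| Index | Later | SAP class |
|---|---|---|
| No attendance | Part-time | improvement |
| No attendance | Full-time | improvement |
| Part-time | Full-time | improvement |
| Part-time | No attendance | worsening |
| Full-time | Part-time | worsening |
| Full-time | No attendance | worsening |

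Three shifts are improvement, three are worsening, and none is neutral. Only an unchanged category is left as stable. Age and reason appear nowhere.

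**2. Age-expected transitions under the rule.**
- *No attendance* at index, then starting pre-school or school: row 1 or 2, improvement.
- *Full-time* at index, then completing school: row 6, worsening.
- *Full-time* pre-school, then *Full-time* school: unchanged, stable.
- No status recorded at a time point: not reported (SAP 3.6.2).

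**3. Time available.** Inclusion requires a start by 23-Sep-2019, and the cut-off is 09-Mar-2020: 168 days / 7 = 24 weeks. That is the shortest potential follow-up. The Week 52 window opens at 40 weeks, and 40 × 7 = 280 days before the cut-off is 03-Jun-2019, so patients who started after that date cannot contribute to it. For those with longer follow-up, SAP 3.3 adds further windows: "After week 52 intervals of approximately 11 weeks (e.g. 63 weeks, 74 weeks, etc.) with a time window of +/- 5 weeks will be used". Data also stop 30 days after discontinuation. The opportunity for an age-expected shift therefore varies by patient, and the documents do not give its distribution.

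**4. Leverage of one shift.** Change in a tabulated percentage = 100 × k / n, where k is the number of age-expected shifts and n the number assessed. The documents give neither. Protocol 6.6 uses 50 patients for its precision table; smaller n are assumed.

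| n assessed | k = 1 | k = 3 |
|---|---|---|
| 20 | 5.0 points | 15.0 points |
| 30 | 3.3 points | 10.0 points |
| 50 | 2.0 points | 6.0 points |

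Entries and completions oppose each other only in a net comparison. Improvement and worsening are reported as separate percentages, so an entry raises the first and a completion raises the second.

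**The case against.** The strongest reply is that the effect may be small and is partly visible already. A by-patient listing in a study expecting about 50 to 65 patients can be read line by line, and SAP 3.6 also feeds the attendance data into physician narratives. This is one component of one of ten secondary objectives, all descriptive and untested. The eCRF is not among the documents, so a 'not applicable' code for very young children cannot be ruled out, and some may have no status recorded at all. All of this stands, and it makes the point minor. It does not alter the rule, and a listing does not change what the table shows.

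Some stronger readings are tempting but unsupported:

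- **A rate of false improvement.** A reader might convert the age bands into a rate: with ages uniform over 2-5 (208 weeks) and one entry age, 24/208 = 12% by Week 24 and 52/208 = 25% by Week 52; with ages uniform over 12-17 (312 weeks) and leaving at 18, 52/312 = 17%. These are near-upper illustrations within single bands. They need every child's recorded status to change at the threshold, nothing missing, and follow-up that not all patients have. The documents support none of these conditions.
- **A bias in favour of alpelisib.** Entry and completion pull opposite ways and the age mix is not given, so the net sign is unknown.
- **Percentages that carry no functional information.** The text shows contamination of unknown degree and no more.
- **The same fault in adult work attendance.** The work rule also ignores the reason, but the documents show no ageing mechanism there.

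**Conclusion.** The point holds in a limited form. Followed as written, SAP 3.6 can count school entry as improvement and school completion as worsening, and its table gives no means of separating them from functional change. This rests on the definitions alone, plus the condition that a patient who makes such a transition has an attendance category recorded at index and afterwards. Its size cannot be derived from the documents. On the assumed 20 to 50 patients assessed, each such shift is worth 5 to 2 percentage points in the row it enters. The primary endpoint is unaffected, and since no secondary endpoint is tested, no error rate is involved. It is a minor matter of presentation and interpretation.

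**What to change.** Keep the shift rule and keep all patients, including those in pre-school. In SAP 3.6 and Table 3-6:

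1. Cross-tabulate improvement and worsening by recorded reason, with four rows: PROS- or health-related; age-expected school entry or completion; other; not recorded. This returns the reason to the table, as protocol 6.8.2 planned.
2. Show attendance by the age bands already listed in SAP 3.5.4.
3. Assign the rows from the recorded reason, not from an assumed school-entry age. The access program covers 14 countries (protocol section 4), and entry ages may differ between them.

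Two more drastic changes are not recommended. Dropping children below school-entry age would conflict with the protocol, whose objective 7 includes pre-school. Counting only PROS-attributed shifts would make the result depend on incomplete, retrospectively abstracted attribution.

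The cost is a wording change and one extra classification of data already planned for a listing. The planned overall percentages stay as they are. The drawbacks are small cells and a *not recorded* row that may be sizeable, because reasons are available only for some patients.
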